The indicators in this part are mainly descriptive. Statistical analysis methods are the same as those in 7.1.

7.5 Follow-up data

The follow-up data include the frontal/lateral X-ray examination of fracture sites 1 week, 6 weeks, 12 weeks and 24 weeks after surgery, SF-12v2 health assessment scale, EQ5D and Harris hip score.

For indicators related to follow-up data, descriptive analysis is mainly performed. Statistical analysis methods are the same as those in 7.1.

7.6 Laboratory examinations

Laboratory test indicators include complete blood count and blood biochemical test. Blood test includes white blood cell (WBC), neutrophil percentage, red blood cell (RBC), hemoglobin, platelet, international normalized ratio (INR) and activated partial thromboplastin time (APTT); blood biochemical test includes alanine aminotransferase (ALT), aspartate aminotransferase (AST), albumin (ALB), cholesterol (CHOL), triglyceride (TRIG), creatinine (CREA), blood urea nitrogen (BUN), urea (UREA), uric acid (UA), low density lipoprotein (LDL-C), high-density lipoprotein (HDL-C), blood glucose (GLU), C-reactive protein (CRP) and hypersensitive CRP.

As for the laboratory examination indicators, the outcomes immediately after surgery relative to the preoperative conditions will be given. There are mainly five cases listed, including "Normal \rightarrow Abnormal (with clinical significance)", "Normal \rightarrow Abnormal (without clinical significance)", "Normal \rightarrow Normal", "Abnormal \rightarrow Abnormal"; the descriptive analysis method is mainly adopted. Statistical analysis methods are the same as those in 7.1. Meanwhile, the list of subjects presenting "Normal \rightarrow Abnormal (with clinical significance)" will be given, including laboratory examination indicators, site number, random number, group, age, gender, and laboratory indicator test values before surgery and immediately after surgery.

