6.6 Significant level and statistical analysis software

For the primary endpoint, statistical analysis will be performed at the one-sided 0.025 significance level (corresponding to the one-sided confidence limit of the 95% confidence interval). For other endpoints, all statistical analysis will be performed at the two-sided 0.05 significance level (except for special instructions). SAS[®] 9.4 statistical software will be used for statistical analysis.

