7.1 Demographic indicators and other baseline indicators

Demographic data include gender, age, height, weight and BMI; other baseline indicators include the subject's medical history, SF-12v2 questionnaire, EQ-5D questionnaire and preoperative fracture status.

Where:

Age = (Date of informed consent - Date of birth)/365.25;

BMI = Body weight $(kg)/(\text{Height }(m))^2$.

The indicators in this part are mainly descriptive. Enumeration data are described by frequency and composition ratio, while measurement data are described by mean, standard deviation, median, quartile, maximum and minimum. The likelihood ratio Chi-square test will be used to compare the enumeration data between groups. Fisher's exact probability test will be used when the theoretical frequency in the fourfold table is less than 5.

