2. Group t-test or Wilcoxon rank-sum test is used to analyze the intergroup comparison of quantitative indicators.

3. In quantitative indicators, Q1: 25th quantile, Q3: 75th percentile.

4. Age = (Date of informed consent - Date of birth)/365.25;

	•	•	-	0
Indicator	Study group	Control group	Statistics	P value
Body weight (kg)				
Number of subjects (N miss)	XXX (XXX)	XXX (XXX)X.XXXX	X.XXXX	
Mean \pm SD	$XX.XX \pm XX.XX$	$XX.XX \pm XX.XX$		
Median	XX.XX	XX.XX		
Q1;Q3	XX.XX ;XX.XX	XX.XX ;XX.XX		
Minimum; maximum	XX.XX ;XX.XX	XX.XX ;XX.XX		
Height (cm)				
Number of subjects (N miss)	XXX (XXX)	XXX (XXX)	X.XXXX	X.XXXX
Mean \pm SD	$XX.XX \pm XX.XX$	$XX.XX \pm XX.XX$		
Median	XX.XX	XX.XX		
Q1;Q3	XX.XX ;XX.XX	XX.XX ;XX.XX		
Minimum; maximum	XX.XX ;XX.XX	XX.XX ;XX.XX		
BMI(kg/m^2)				
Number of subjects (N miss)	XXX (XXX)	XXX (XXX)	X.XXXX	X.XXXX
Mean ± SD	XX.XX ±XX.XX	XX.XX ±XX.XX		
Median	XX.XX	XX.XX		
Q1;Q3	XX.XX ;XX.XX	XX.XX ;XX.XX		
Minimum; maximum	XX.XX;XX.XX	XX.XX ;XX.XX		

Table 15 Statistical analysis results of subjects' height and body weight

- Notes: 1. Group t-test or Wilcoxon rank-sum test is used to analyze the intergroup comparison of quantitative indicators.
 - 2. In quantitative indicators, Q1: 25th quantile, Q3: 75th percentile.
 - 3. BMI= Body weight (kg)/Height (m)2;

Indicator	Study group	Control group	Statistics	P value
Osteoporosis				
Number of subjects (N miss)	XXX (XXX)	XXX (XXX)	X.XXXX	X.XXXX
Yes	XXX (XX.X%)	XXX (XX.X%)		
No	XXX (XX.X%)	XXX (XX.X%)		
Still persist	()			
Number of subjects (N miss)	XXX (XXX)	XXX (XXX)	X.XXXX	X.XXXX
Yes	XXX (XX.X%)	XXX (XX.X%)		
No	XXX (XX.X%)	XXX (XX.X%)		
Malnutrition				
Number of subjects (N miss)	XXX (XXX)	XXX (XXX)	X.XXXX	X.XXXX
None	XXX (XX.X%)	XXX (XX.X%)		
Ca	XXX (XX.X%)	XXX (XX.X%)		
Р	XXX (XX.X%)	XXX (XX.X%)		
Protein	XXX (XX.X%)	XXX (XX.X%)		
Fe	XXX (XX.X%)	XXX (XX.X%)		
Others	XXX (XX.X%)	XXX (XX.X%)		
Still persist	. ,			
Number of subjects (N miss)	XXX (XXX)	XXX (XXX)	X.XXXX	X.XXXX
Yes	XXX (XX.X%)	XXX (XX.X%)		
No	XXX (XX.X%)	XXX (XX.X%)		
Anemia				
Number of subjects (N miss)	XXX (XXX)	XXX (XXX)	X.XXXX	X.XXXX
Yes	XXX (XX.X%)	XXX (XX.X%)		
No	XXX (XX.X%)	XXX (XX.X%)		
Still persist				
Number of subjects (N miss)	XXX (XXX)	XXX (XXX)	X.XXXX	X.XXXX
Yes	XXX (XX.X%)	XXX (XX.X%)		
No	XXX (XX.X%)	XXX (XX.X%)		
Hormone deficiency				
Number of subjects (N miss)	XXX (XXX)	XXX (XXX)	X.XXXX	X.XXXX
None	XXX (XX.X%)	XXX (XX.X%)		

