$Normal \rightarrow Normal$	XXX (XX.X%)	XXX (XX.X%)		
Abnormal \rightarrow Normal	XXX (XX.X%)	XXX (XX.X%)		
Abnormal \rightarrow Abnormal	XXX (XX.X%)	XXX (XX.X%)		
NE				
Number of subjects (N miss)	XXX (XXX)	XXX (XXX)	X.XXXX	X.XXXX
Normal \rightarrow Abnormal (with clinical significance)	XXX (XX.X%)	XXX (XX.X%)		
Normal \rightarrow Abnormal (without clinical significance)	XXX (XX.X%)	XXX (XX.X%)		
$Normal \rightarrow Normal$	XXX (XX.X%)	XXX (XX.X%)		
Abnormal \rightarrow Normal	XXX (XX.X%)	XXX (XX.X%)		
Abnormal \rightarrow Abnormal	XXX (XX.X%)	XXX (XX.X%)		
Red blood cell (RBC)				
Number of subjects (N miss)	XXX (XXX)	XXX (XXX)	X.XXXX	X.XXXX
Normal \rightarrow Abnormal (with clinical significance)	XXX (XX.X%)	XXX (XX.X%)		
Normal \rightarrow Abnormal (without clinical significance)	XXX (XX.X%)	XXX (XX.X%)		
$Normal \rightarrow Normal$	XXX (XX.X%)	XXX (XX.X%)		
Abnormal \rightarrow Normal	XXX (XX.X%)	XXX (XX.X%)		
Abnormal \rightarrow Abnormal	XXX (XX.X%)	XXX (XX.X%)		
HGB				
Number of subjects (N miss) Normal \rightarrow Abnormal (with	XXX (XXX)	XXX (XXX)	X.XXXX	X.XXXX
clinical significance)	XXX (XX.X%)	XXX (XX.X%)		
Normal \rightarrow Abnormal (without clinical significance)	XXX (XX.X%)	XXX (XX.X%)		
$Normal \rightarrow Normal$	XXX (XX.X%)	XXX (XX.X%)		
Abnormal \rightarrow Normal	XXX (XX.X%)	XXX (XX.X%)		
Abnormal \rightarrow Abnormal	XXX (XX.X%)	XXX (XX.X%)		
Platelet				
Number of subjects (N miss)	XXX (XXX)	XXX (XXX)	X.XXXX	X.XXXX
Normal \rightarrow Abnormal (with clinical significance)	XXX (XX.X%)	XXX (XX.X%)		
Normal \rightarrow Abnormal (without clinical significance)	XXX (XX.X%)	XXX (XX.X%)		
$Normal \rightarrow Normal$	XXX (XX.X%)	XXX (XX.X%)		
$Abnormal \rightarrow Normal$	XXX (XX.X%)	XXX (XX.X%)		
Abnormal \rightarrow Abnormal	XXX (XX.X%)	XXX (XX.X%)		

Table 74 Statistical analysis results of outcomes of subjects' complete blood count before and after surgery (before surgery → immediately after surgery)

Medical Research & Biometrics Center, National Center for Cardiovascular Diseases

Version No.: V1.0

Notes: 1. The likelihood ratio Chi-square test or Fisher's exact probability test is used to analyze the intergroup comparison of qualitative indicators;

Table 74 Statistical analysis results of outcomes of subjects' complete blood count before and after surgery (before surgery → immediately after surgery) (continued)

Indicator	Study group	Control group	Statistics	P value	
INR					

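### Twenty-one measured laboratory values are compared between arms only as Normal/Abnormal shift categories, so the size of change is never summarised and precision is lost

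*SAP*

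**What the plan says.** SAP 7.6 lists 7 blood-count and coagulation measures and 14 biochemistry measures, 21 in all. For these, "As for the laboratory examination indicators, the outcomes immediately after surgery relative to the preoperative conditions will be given", and "the descriptive analysis method is mainly adopted. Statistical analysis methods are the same as those in 7.1".

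The text announces the categories with "There are mainly five cases listed, including" but then names four. The shells of Tables 74 and 76 supply the fifth, Abnormal to Normal. Each analyte has those five rows, a statistic and a P value. The table note reads: "The likelihood ratio Chi-square test or Fisher's exact probability test is used to analyze the intergroup comparison of qualitative indicators". SAP 7.1 gives the same rule: "The likelihood ratio Chi-square test will be used to compare the enumeration data between groups", with Fisher's test for small expected counts.

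Measured results are printed in one place only. Tables 75 and 77 list "laboratory indicator test values before surgery and immediately after surgery", restricted to subjects who moved from normal to a clinically significant abnormality.

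The plan handles other continuous data differently:
- Protocol 10.10.1 and SAP 7.1 both call for mean, SD, median and range (SAP 7.1 adds quartiles).
- Notes under other tables say "Group t-test or Wilcoxon rank-sum test is used to analyze the intergroup comparison of quantitative indicators". Blood loss, transfusion volume and drainage (Tables 23 and 24) are reported that way.
- Change in SF-12 and in the EQ-5D index is given with a between-arm difference and 95% CI (Tables 39-42 and 49-52).

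**The concern.** A shift category records which side of a limit a result falls on and discards how far it moved. For subjects already abnormal before surgery, worsening, no change and partial improvement all fall in the same row. The listings do not recover the first group, because they begin from a normal pre-operative result. Movement inside the normal range is lost as well. A reader of the report could not say how far haemoglobin, creatinine or CRP moved in either arm, or by how much the arms differed.

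At stake is the usefulness of the laboratory safety tables. Their only inferential output is one P value per analyte from a test that ignores magnitude, with no estimate or interval beside it.

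**Working it through.** **Step 1: the plan's own figure.** The only sample size stated is for the primary endpoint (SAP 6.2: 95% union in both arms, margin 0.10, power 80%; SAP 6.6: one-sided 0.025).
n = (1.960 + 0.842)² × (2 × 0.95 × 0.05) / 0.10² = 7.85 × 0.095 / 0.01 = 74.6, so 75 per arm; 75 / 0.80 = 93.75, so 94 per arm. Both match. Nothing comparable exists for laboratory data: no effect size, SD, proportion abnormal or pre/post correlation is given. Everything from Step 3 on therefore rests on assumptions.

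**Step 2: what the outputs show, without simulation.**

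| Before | After | Row in Tables 74/76 | In Tables 75/77? |
|---|---|---|---|
| Abnormal | Much worse | Abnormal to Abnormal | No |
| Abnormal | Unchanged | Abnormal to Abnormal | No |
| Abnormal | Back in range | Abnormal to Normal | No |
| Normal | Clinically significant abnormality | Separate row | Yes, with values |

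The first two cannot be told apart anywhere in the laboratory output.

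**Step 3: power for a moderate shift.** Assumed: 94 complete pairs per arm; bivariate normal pre and post values; correlation r = 0.3, 0.5 or 0.7; 5-50% abnormal before and 10-70% after surgery; 30% of post-operative abnormals clinically significant. The level is two-sided 0.05 ("For other endpoints, all statistical analysis will be performed at the two-sided 0.05 significance level"). The arm shift is set so that a t-test on the post-operative value has 80% power: d = (1.960 + 0.842) × √(2/94) = 0.409 SD. Each scenario has 1,000 simulated trials.

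- t-test on the post-operative value: 77-82%.
- ANCOVA adjusted for the pre-operative value: 81-98%. Formula check, Φ(d√(n/2)/√(1 − r²) − 1.960) with d√(n/2) = 2.80: 84%, 90% and 98% for r = 0.3, 0.5 and 0.7.
- Likelihood-ratio test on the five categories: 30-57%.
- Mid-range case (r = 0.5, 20% abnormal before, 30% after): 45% for the categories, 79% for the t-test, 90% for ANCOVA. Relative loss against ANCOVA: 1 − 0.45/0.90 = 50%.
- Over the grid the relative loss is 28-63% against the t-test and 41-64% against ANCOVA.

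A second grid (0.4 SD shift, r = 0.3 or 0.6, 20-70% abnormal before surgery, clinically significant meaning more than 1 SD beyond the limit, 800 trials per scenario) gave 25-52% against 80-95% for ANCOVA; a rerun gave 22-51% against 80-94%. Taken together: about 25-57% against about 80-98%.

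**Step 4: dependence on the size of the shift** (94 per arm, r = 0.5; two prevalence cases, 20% then 50% abnormal and 10% then 20% abnormal).

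| Shift (SD) | Categories | t-test | ANCOVA | Loss against ANCOVA |
|---|---|---|---|---|
| 0.286 | 25%, 21% | 47%, 50% | 61%, 63% | 58%, 66% |
| 0.473 | 65%, 55% | 90%, 91% | 96%, 95% | 33%, 42% |
| 0.625 | 89%, 80% | 99%, 99% | 100%, 100% | 11%, 20% |

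**Step 5: limits of the check.** With no true difference the likelihood-ratio test rejected 6.6-7.1% of the time, so its power above is slightly flattered. Fisher's test and a site term were not simulated. With 75 per arm (shift 0.457 SD) the category test has 34-56%.

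**The case against.** The strongest reply is that nothing planned is being lost. Laboratory values are not among the primary or secondary endpoints, 7.6 calls itself mainly descriptive, and no laboratory hypothesis or power is stated. Shift tables with a clinical-significance flag answer a natural safety question, and a 0.4 SD mean shift need not matter clinically. By pointing to 7.1, section 7.6 already imports a rule for describing measurement data; only the shells leave it out. All of this stands, and it keeps the point small. It does not remove it: the shells decide what is reported, and they print a P value for every analyte rather than description alone.

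A reader might infer more than the documents support:

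- **That half of the laboratory power is lost.** That is one mid-range result under an assumed moderate shift. The loss depends on analyte and effect size, and no single figure follows from the plan.
- **That a real difference cannot be seen when most subjects start abnormal.** The Abnormal to Normal row still registers recovery, and the category test keeps some power in every scenario examined. At 0.8 SD in the second grid it had 86-99% in 10 of 12 scenarios and 65-71% in the other two.
- **That these tables are the only objective systemic safety comparison.** Protocol 8.2 counts abnormal laboratory findings as adverse events, and the SAP compares AEs, SAEs, device-related events and UADEs between arms with rate differences and 95% CIs. Blood loss and transfusion volume are already compared as measured values.
- **That better analysis would settle the safety of the new alloy.** The protocol schedule provides one post-operative sample, taken in the recovery phase under site standard of care. It mainly reflects surgery and says little about longer exposure.

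On multiplicity, 21 comparisons carry about a 66% chance of at least one false positive if independent (1 − 0.95²¹). The present 21 P values have the same problem, so reporting estimates in their place adds none.

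**Conclusion.** The point holds as a low-cost improvement. For all 21 analytes the only between-arm comparison is on shift categories, the measured values are neither summarised nor compared, and worsening from an abnormal baseline is invisible in the laboratory outputs. This is inconsistent with Protocol 10.10.1, SAP 7.1 and the SAP's own handling of other continuous measures. For a shift of about 0.4 SD at 94 per arm, power is about 25-57% on the categories and about 80-98% with baseline adjustment. The gap narrows to roughly 11-20% in relative terms at 0.625 SD. These figures rest on assumed normality, correlations, abnormal proportions and complete pairs, none of which the documents give. No primary or listed secondary conclusion changes.

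**What to change.** In SAP 7.6 and the shells of Tables 74 and 76:

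1. For each analyte, add n, mean, SD, median and quartiles by arm, before surgery, after surgery and for the change.
2. Add the between-arm difference in the post-operative value with a 95% CI, adjusted for the pre-operative value and for site, with small sites merged as in SAP 6.7. Use the log scale for skewed analytes such as CRP and ALT. Label it exploratory safety estimation, with no multiplicity claim.
3. Keep the shift categories and the listings in Tables 75 and 77 as description, and drop the P value from the shift tables.
4. Make the 7.6 text name all five categories, so that it agrees with the shells.

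The cost is a few more programmed tables from data already collected, with no new visit or sample. Units must be harmonised across hospital laboratories; the site term absorbs differences in level but not in units. The unfixed timing of the post-operative sample adds noise that the analysis cannot remove, and incomplete pairs would reduce the numbers, so n should be shown for every analyte.

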7.7 Concomitant medication, adverse events (AEs) or serious adverse events

(SAEs)

For concomitant medication, the subject's concomitant medication is provided in the form of a list.

The AEs and investigational device-related AEs in subjects will be tabulated and summarized, respectively. The list of subjects reported with AEs/ investigational device-related AEs includes site number, random number, group, age, gender, name of AE (SOC code), name of AE (PT code), time of postoperative occurrence (day), remission time (day), severity, measures taken, outcome, correlation with surgery, correlation with investigational device, withdrawal from the trial due to AEs, whether it is unanticipated adverse device effect (UADE), device failure or SAE.

Investigational device-related AEs refer to those "definitely related", "probably related" and "possibly related" with the investigational device;

Time of postoperative occurrence (day) = Date of occurrence of AE - Date of surgery,

Remission time (day) = End date of AE - Date of occurrence of AE.

The summary form will list the total number of cases of AEs/investigational device-related AEs, the total number of subjects suffering from AEs/investigational device-related AEs.

Wherein, the total case of AEs refers to the number of subjects suffering from AEs, and the AEs occur in the subject at least one time, which is considered as "Yes";

Statistical analysis of the severity of adverse events, the relationship with the study device and the relationship with the surgery was performed. If multiple adverse events occurred in a patient, the analysis was performed with the most severe or highest correlation.

The SAEs and investigational device-related SAEs in subjects will be tabulated and summarized, respectively; such data will be presented in the same form as AEs. The list of subjects reported with SAEs/investigational device-related SAEs includes site number, random number, group, age, gender, name of SAE (SOC code), name of SAE (PT code), time of postoperative occurrence (day), remission time (day), severity, outcome, correlation with surgery, correlation with investigational device and SAE.

The list and summary of UADEs in subjects will be presented respectively in the same form as AEs.

The calculation method of the time of postoperative occurrence (day) and remission time (day), the presentation of the summary form and the statistical principle are the same as those for AEs.

Randomization (N=XXX) Control group Study group (N=XXX) (N=XXX) No investigational device is implanted Study group: N₁=XXX Control group: N₂=XXX FAS FAS (N=XXX) (N=XXX) Serious protocol violation (Study group: N1=XXX, Control group: N₂=XXX): 1. Loss to follow-up during the trial (N1=XXX, N₂=XXX) 2. Cross enrollment (N1=XXX, N2=XXX) 3. Use of third party products (N₁=XXX, N₂=XXX) 4. Violation of inclusion and exclusion criteria (N1=XXX, N2=XXX) PPS PPS (N=XXX) (N=XXX) ATS ATS (N=XXX) (N=XXX)

8. Generation of Statistical Graphs, Tables and Lists

Figure 1 Flow chart for determination of analysis population data sets

Indicator	Study group	Control group
Randomization	XXX (XX.X%)	XXX (XX.X%)
No investigational device is implanted	XXX (XX.X%)	XXX (XX.X%)
Serious protocol violation		
Violation of inclusion and exclusion criteria	XXX (XX.X%)	XXX (XX.X%)
Loss to follow-up during the trial	XXX (XX.X%)	XXX (XX.X%)
Cross enrollment	XXX (XX.X%)	XXX (XX.X%)
Use of third party products	XXX (XX.X%)	XXX (XX.X%)
Out-of-specification use of investigational products	XXX (XX.X%)	XXX (XX.X%)
Out-of-window time	XXX (XX.X%)	XXX (XX.X%)
FAS	XXX (XX.X%)	XXX (XX.X%)
PPS	XXX (XX.X%)	XXX (XX.X%)
ATS	XXX (XX.X%)	XXX (XX.X%)

Table 1Determination of analysis population

Notes: 1. FAS = Number of subjects enrolled randomly - Number of subjects not implanted with any investigational device;

2. Number of subjects who seriously violate the protocol = Violation of inclusion and exclusion criteria + Loss to follow-up during the trial + Cross enrollment + Use of third party products + Out-of-specification use of investigational products + Out-of-window time;

3. PPS = FAS - Number of subjects who seriously violate the protocol; ATS = PPS + Number of cross-enrolled subjects alone;

4. No investigational device is implanted means that the subject has been given a random number but has not received any study-related treatment;

Loss to follow-up during the trial refers to the situation in which the fracture union rate 24 weeks after the primary endpoint surgery is not available;

Cross enrollment refers to the situation in which subjects randomly assigned to the study group receive the control products, while subjects randomly assigned to the control group receive the investigational products;

Out-of-specification use of investigational products refers to the situation in which the specification of the device implanted in the subject is not within the specification range specified in the study protocol;

Use of third party products refers to the situation in which the subjects randomly assigned to the study group or the control group use third party products;

Out-of-window time refers to the situation in which the difference between the follow-up date at 24 weeks after subjects have received the primary endpoint surgery and the surgery date do not fall within the range of [140, 196], and this protocol violation may seriously affect the results of primary efficacy endpoints;

Table 2List of subjects who withdrawal the informed consent or
seriously violate the protocol

Site No.	Random No.	Group	Gender	Age	Туре	Reason	FAS	PPS	ATS
XXX	XXX	XXX	XXX	XXX					
XXX	XXX	XXX	XXX	XXX					

Note: If the subject is included in FAS, PPS and ATS, mark with " $\sqrt{}$ "; if the subject is not included in FAS, PPS and ATS, mark with " \times ".

-

_

Site No.	Random No.	Group	Gender	Age	Туре	AE/SAE related or not	Withdrawal of subjects from the trial or not
XXX	XXX	XXX	XXX	XXX			
XXX	XXX	XXX	XXX	XXX			

Table 3 List of subjects who violate the protocol (CRF collection)

Indicator	Study group	Control group
Randomization	XXX (XX.X%)	XXX (XX.X%)
No investigational device is implanted	XXX (XX.X%)	XXX (XX.X%)
Serious protocol violation		
Violation of inclusion and exclusion criteria	XXX (XX.X%)	XXX (XX.X%)
Loss to follow-up during the trial	XXX (XX.X%)	XXX (XX.X%)
Cross enrollment	XXX (XX.X%)	XXX (XX.X%)
Use of third party products	XXX (XX.X%)	XXX (XX.X%)
Out-of-specification use of investigational products	XXX (XX.X%)	XXX (XX.X%)
Out-of-window time	XXX (XX.X%)	XXX (XX.X%)
FAS	XXX (XX.X%)	XXX (XX.X%)
PPS	XXX (XX.X%)	XXX (XX.X%)
ATS	XXX (XX.X%)	XXX (XX.X%)

Table 4Determination of analysis population in Beijing JishuitanHospital

Notes: 1. FAS = Number of subjects enrolled randomly - Number of subjects not implanted with any investigational device;

2. Number of subjects who seriously violate the protocol = Violation of inclusion and exclusion criteria + Loss to follow-up during the trial + Cross enrollment + Use of third party products + Out-of-specification use of investigational products + Out-of-window time;

3. PPS = FAS - Number of subjects who seriously violate the protocol; ATS = PPS + Number of cross-enrolled subjects alone;

4. No investigational device is implanted means that the subject has been given a random number but has not received any study-related treatment;

Loss to follow-up during the trial refers to the situation in which the fracture union rate 24 weeks after the primary endpoint surgery is not available;

Cross enrollment refers to the situation in which subjects randomly assigned to the study group receive the control products, while subjects randomly assigned to the control group receive the investigational products;

Out-of-specification use of investigational products refers to the situation in which the specification of the device implanted in the subject is not within the specification range specified in the study protocol;

Use of third party products refers to the situation in which the subjects randomly assigned to the study group or the control group use third party products;

Out-of-window time refers to the situation in which the difference between the follow-up date at 24 weeks after subjects have received the primary endpoint surgery and the surgery date do not fall within the range of [140, 196], and this protocol violation may seriously affect the results of primary efficacy endpoints;

Indicator	Study group	Control group
Randomization	XXX (XX.X%)	XXX (XX.X%)
No investigational device is implanted	XXX (XX.X%)	XXX (XX.X%)
Serious protocol violation		
Violation of inclusion and exclusion criteria	XXX (XX.X%)	XXX (XX.X%)
Loss to follow-up during the trial	XXX (XX.X%)	XXX (XX.X%)
Cross enrollment	XXX (XX.X%)	XXX (XX.X%)
Use of third party products	XXX (XX.X%)	XXX (XX.X%)
Out-of-specification use of investigational products	XXX (XX.X%)	XXX (XX.X%)
Out-of-window time	XXX (XX.X%)	XXX (XX.X%)
FAS	XXX (XX.X%)	XXX (XX.X%)
PPS	XXX (XX.X%)	XXX (XX.X%)
ATS	XXX (XX.X%)	XXX (XX.X%)

Table 5 **Determination of analysis population in Peking University Third** Hospital

Notes:

1. FAS = Number of subjects enrolled randomly - Number of subjects not implanted with any investigational device;

2: Number of subjects who seriously violate the protocol = Violation of inclusion and exclusion criteria + Loss to follow-up during the trial + Cross enrollment + Use of third party products + Out-of-specification use of investigational products + Out-of-window time;

3. PPS = FAS - Number of subjects who seriously violate the protocol; ATS = PPS + Numberof cross-enrolled subjects alone;

4. No investigational device is implanted means that the subject has been given a random number but has not received any study-related treatment;

Loss to follow-up during the trial refers to the situation in which the fracture union rate 24 weeks after the primary endpoint surgery is not available;

Cross enrollment refers to the situation in which subjects randomly assigned to the study group receive the control products, while subjects randomly assigned to the control group receive the investigational products;

Out-of-specification use of investigational products refers to the situation in which the specification of the device implanted in the subject is not within the specification range specified in the study protocol;

Use of third party products refers to the situation in which the subjects randomly assigned to the study group or the control group use third party products;

Out-of-window time refers to the situation in which the difference between the follow-up date at 24 weeks after subjects have received the primary endpoint surgery and the surgery date do not fall within the range of [140, 196], and this protocol violation may seriously affect the results of primary efficacy endpoints;

Indicator	Study group	Control group
Randomization	XXX (XX.X%)	XXX (XX.X%)
No investigational device is implanted	XXX (XX.X%)	XXX (XX.X%)
Serious protocol violation		
Violation of inclusion and exclusion criteria	XXX (XX.X%)	XXX (XX.X%)
Loss to follow-up during the trial	XXX (XX.X%)	XXX (XX.X%)
Cross enrollment	XXX (XX.X%)	XXX (XX.X%)
Use of third party products	XXX (XX.X%)	XXX (XX.X%)
Out-of-specification use of investigational products	XXX (XX.X%)	XXX (XX.X%)
Out-of-window time	XXX (XX.X%)	XXX (XX.X%)
FAS	XXX (XX.X%)	XXX (XX.X%)
PPS	XXX (XX.X%)	XXX (XX.X%)
ATS	XXX (XX.X%)	XXX (XX.X%)

Table 6Determination of analysis population in Chinese PLA General
Hospital

Notes: 1. FAS = Number of subjects enrolled randomly - Number of subjects not implanted with any investigational device;

2: Number of subjects who seriously violate the protocol = Violation of inclusion and exclusion criteria + Loss to follow-up during the trial + Cross enrollment + Use of third party products + Out-of-specification use of investigational products + Out-of-window time;

3. PPS = FAS - Number of subjects who seriously violate the protocol; ATS = PPS + Number of cross-enrolled subjects alone;

4. No investigational device is implanted means that the subject has been given a random number but has not received any study-related treatment;

Loss to follow-up during the trial refers to the situation in which the fracture union rate 24 weeks after the primary endpoint surgery is not available;

Cross enrollment refers to the situation in which subjects randomly assigned to the study group receive the control products, while subjects randomly assigned to the control group receive the investigational products;

Out-of-specification use of investigational products refers to the situation in which the specification of the device implanted in the subject is not within the specification range specified in the study protocol;

Use of third party products refers to the situation in which the subjects randomly assigned to the study group or the control group use third party products;

Out-of-window time refers to the situation in which the difference between the follow-up date at 24 weeks after subjects have received the primary endpoint surgery and the surgery date do not fall within the range of [140, 196], and this protocol violation may seriously affect the results of primary efficacy endpoints;

Table 7

Hospital of Zhejiang University School of Medicine		
Indicator	Study group	Control group
D 1		

Determination of analysis nonulation in the Second Affiliated

Indicator	Study group	Control group
Randomization	XXX (XX.X%)	XXX (XX.X%)
No investigational device is implanted	XXX (XX.X%)	XXX (XX.X%)
Serious protocol violation		
Violation of inclusion and exclusion criteria	XXX (XX.X%)	XXX (XX.X%)
Loss to follow-up during the trial	XXX (XX.X%)	XXX (XX.X%)
Cross enrollment	XXX (XX.X%)	XXX (XX.X%)
Use of third party products	XXX (XX.X%)	XXX (XX.X%)
Out-of-specification use of investigational	XXX (XX.X%)	XXX (XX.X%)
products		
Out-of-window time	XXX (XX.X%)	XXX (XX.X%)
FAS	XXX (XX.X%)	XXX (XX.X%)
PPS	XXX (XX.X%)	XXX (XX.X%)
ATS	XXX (XX.X%)	XXX (XX.X%)

Notes: 1. FAS = Number of subjects enrolled randomly - Number of subjects not implanted with any investigational device;

2: Number of subjects who seriously violate the protocol = Violation of inclusion and exclusion criteria + Loss to follow-up during the trial + Cross enrollment + Use of third party products + Out-of-specification use of investigational products + Out-of-window time;

3. PPS = FAS - Number of subjects who seriously violate the protocol; ATS = PPS + Number of cross-enrolled subjects alone;

4. No investigational device is implanted means that the subject has been given a random number but has not received any study-related treatment;

Loss to follow-up during the trial refers to the situation in which the fracture union rate 24 weeks after the primary endpoint surgery is not available;

Cross enrollment refers to the situation in which subjects randomly assigned to the study group receive the control products, while subjects randomly assigned to the control group receive the investigational products;

Out-of-specification use of investigational products refers to the situation in which the specification of the device implanted in the subject is not within the specification range specified in the study protocol;

Use of third party products refers to the situation in which the subjects randomly assigned to the study group or the control group use third party products;

Out-of-window time refers to the situation in which the difference between the follow-up date at 24 weeks after subjects have received the primary endpoint surgery and the surgery date do not fall within the range of [140, 196], and this protocol violation may seriously affect the results of primary efficacy endpoints;

Indicator	Study group	Control group
Randomization	XXX (XX.X%)	XXX (XX.X%)
No investigational device is implanted	XXX (XX.X%)	XXX (XX.X%)
Serious protocol violation		
Violation of inclusion and exclusion criteria	XXX (XX.X%)	XXX (XX.X%)
Loss to follow-up during the trial	XXX (XX.X%)	XXX (XX.X%)
Cross enrollment	XXX (XX.X%)	XXX (XX.X%)
Use of third party products	XXX (XX.X%)	XXX (XX.X%)
Out-of-specification use of investigational products	XXX (XX.X%)	XXX (XX.X%)
Out-of-window time	XXX (XX.X%)	XXX (XX.X%)
FAS	XXX (XX.X%)	XXX (XX.X%)
PPS	XXX (XX.X%)	XXX (XX.X%)
ATS	XXX (XX.X%)	XXX (XX.X%)

Table 8Determination of analysis population in Shanghai General
Hospital

Notes: 1. FAS = Number of subjects enrolled randomly - Number of subjects not implanted with any investigational device;

2: Number of subjects who seriously violate the protocol = Violation of inclusion and exclusion criteria + Loss to follow-up during the trial + Cross enrollment + Use of third party products + Out-of-specification use of investigational products + Out-of-window time;

3. PPS = FAS - Number of subjects who seriously violate the protocol; ATS = PPS + Number of cross-enrolled subjects alone;

4. No investigational device is implanted means that the subject has been given a random number but has not received any study-related treatment;

Loss to follow-up during the trial refers to the situation in which the fracture union rate 24 weeks after the primary endpoint surgery is not available;

Cross enrollment refers to the situation in which subjects randomly assigned to the study group receive the control products, while subjects randomly assigned to the control group receive the investigational products;

Out-of-specification use of investigational products refers to the situation in which the specification of the device implanted in the subject is not within the specification range specified in the study protocol;

Use of third party products refers to the situation in which the subjects randomly assigned to the study group or the control group use third party products;

Out-of-window time refers to the situation in which the difference between the follow-up date at 24 weeks after subjects have received the primary endpoint surgery and the surgery date do not fall within the range of [140, 196], and this protocol violation may seriously affect the results of primary efficacy endpoints;

Southern wiedical Oniversity		
Indicator	Study group	Control group
Randomization	XXX (XX.X%)	XXX (XX.X%)
No investigational device is implanted	XXX (XX.X%)	XXX (XX.X%)
Serious protocol violation		
Violation of inclusion and exclusion criteria	XXX (XX.X%)	XXX (XX.X%)
Loss to follow-up during the trial	XXX (XX.X%)	XXX (XX.X%)
Cross enrollment	XXX (XX.X%)	XXX (XX.X%)
Use of third party products	XXX (XX.X%)	XXX (XX.X%)
Out-of-specification use of investigational products	XXX (XX.X%)	XXX (XX.X%)
Out-of-window time	XXX (XX.X%)	XXX (XX.X%)
FAS	XXX (XX.X%)	XXX (XX.X%)
PPS	XXX (XX.X%)	XXX (XX.X%)
ATS	XXX (XX.X%)	XXX (XX.X%)

Table 9Determination of analysis population in Nanfang Hospital Of
Southern Medical University

Notes: 1. FAS = Number of subjects enrolled randomly - Number of subjects not implanted with any investigational device;

2: Number of subjects who seriously violate the protocol = Violation of inclusion and exclusion criteria + Loss to follow-up during the trial + Cross enrollment + Use of third party products + Out-of-specification use of investigational products + Out-of-window time;

3. PPS = FAS - Number of subjects who seriously violate the protocol; ATS = PPS + Number of cross-enrolled subjects alone;

4. No investigational device is implanted means that the subject has been given a random number but has not received any study-related treatment;

Loss to follow-up during the trial refers to the situation in which the fracture union rate 24 weeks after the primary endpoint surgery is not available;

Cross enrollment refers to the situation in which subjects randomly assigned to the study group receive the control products, while subjects randomly assigned to the control group receive the investigational products;

Out-of-specification use of investigational products refers to the situation in which the specification of the device implanted in the subject is not within the specification range specified in the study protocol;

Use of third party products refers to the situation in which the subjects randomly assigned to the study group or the control group use third party products;

Out-of-window time refers to the situation in which the difference between the follow-up date at 24 weeks after subjects have received the primary endpoint surgery and the surgery date do not fall within the range of [140, 196], and this protocol violation may seriously affect the results of primary efficacy endpoints;

Indicator	Study group	Control group
Randomization	XXX (XX.X%)	XXX (XX.X%)
No investigational device is implanted	XXX (XX.X%)	XXX (XX.X%)
Serious protocol violation		
Violation of inclusion and exclusion criteria	XXX (XX.X%)	XXX (XX.X%)
Loss to follow-up during the trial	XXX (XX.X%)	XXX (XX.X%)
Cross enrollment	XXX (XX.X%)	XXX (XX.X%)
Use of third party products	XXX (XX.X%)	XXX (XX.X%)
Out-of-specification use of investigational products	XXX (XX.X%)	XXX (XX.X%)
Out-of-window time	XXX (XX.X%)	XXX (XX.X%)
FAS	XXX (XX.X%)	XXX (XX.X%)
PPS	XXX (XX.X%)	XXX (XX.X%)
ATS	XXX (XX.X%)	XXX (XX.X%)

Table 10 Determination of analysis population in Affiliated Hospital ofNantong University

Notes: 1. FAS = Number of subjects enrolled randomly - Number of subjects not implanted with any investigational device;

2: Number of subjects who seriously violate the protocol = Violation of inclusion and exclusion criteria + Loss to follow-up during the trial + Cross enrollment + Use of third party products + Out-of-specification use of investigational products + Out-of-window time;

3. PPS = FAS - Number of subjects who seriously violate the protocol; ATS = PPS + Number of cross-enrolled subjects alone;

